##### Screening, Recruitment, and Enrollment

Potentially eligible patients will be identified from the review of the visit reason from the thoracic oncology providers' Epic clinic schedules. Patients who have appointments for outpatient care at Multidisciplinary Thoracic Oncology Program (postoperative clinic visit, any radiation, or oncology visit) will be considered. To identify potentially eligible patients, the study coordinator can review clinical documentation such as the patient's chart in the electronic medical record, clinical schedules, or ask clinical staff about potential eligible patients through a limited HIPAA waiver from the IRB. Providers will also be approached by the study coordinator to identify any other patients with lung cancer.

Identified patients will be entered into a screening log. Providers will be asked to verify a clinical diagnosis of lung cancer. For surgical patients, lack of enrollment in concurrent LCCC protocol #1945 will be verified with the assigned study coordinator. Patients meeting the eligibility criteria on the initial screening will be approached in person, by telephone by the study coordinator to verify the remainder of the eligibility criteria and invite the patient to the study. Interested patients will undergo informed consent procedures. An IRB-approved study team member will approach the patient to discuss study procedures, benefits, risks and obtain informed consent prior to any study procedures. Patients who agree to participate will review and sign the informed consent form after the study is explained and questions have been answered.

Patients who are found to be ineligible during screening due to lack of email, phone number, or English language or those potentially eligible during screening but found to be ineligible after contact will be excluded from the study. The reasons for exclusion as well as basic demographics available in the EMR (e.g. race, ethnicity, age, gender, education level if available) will be collected in REDCap.

For patients who are eligible but refuse enrollment, reasons for refusal, as well as basic demographics available in the EMR (e.g. race, ethnicity, age, gender, education level if available) will also be collected within REDCap.

#### Provider Alerts and Reports

Members of the MTOP care team(s) will be assigned to each participant within the Moovcare® portal. ePRO survey symptoms that are severe and/or meet the Moovcare® algorithm for lung cancer recurrence prediction will generate an email alert to a designated clinical care team member. Any free text addressing “other” symptoms will also generate an email alert. The care team will follow their usual protocols for management of symptoms which may include calling patient for more information or to manage the issue, scheduling an appointment or testing, and/or referring to the emergency room amongst other management strategies. At any time, the MTOP care team members can review an assigned participant’s record to determine whether an alert is present and to review the prior ePRO symptom survey responses. If the providers did not view the alert in 48 hours, patients will get a message to contact their health care provider. The unattended alerts will also be escalated to the research coordinator who will communicate it with the clinical team. The study coordinator will have access to all enrolled participants’ Moovcare® records to facilitate review of results.

#### Outcome Surveys

At enrollment, all participants will be trained by the study coordinator how to use the UNC REDCap online system to complete outcomes surveys for the trial. The outcomes surveys will be completed by all participants at baseline; HRQOL will be reassessed at months 3, 6/off-study (+/- 4 weeks each) and patient satisfaction at 6 months/off-study (+/-4 weeks). Participants will be given a choice to complete from home electronically, or if necessary, in clinic at otherwise scheduled routine follow-up visits which occur at least every 3 months or via phone call (with the study coordinator entering the data after participant paper completion into REDCap). For home electronic completion, the outcomes surveys will be sent when due by email via REDCap. The REDCap will send automatic reminders for incomplete surveys. If the patient does not self-complete this information, the study coordinator also has the option to call or email them to collect the information and then enter it into REDCap. If the patient goes off study prior to week 26, the study coordinator will contact the patient as soon as possible to get the off-study surveys completed.

The patient outcomes surveys include:

- **Participant Demographics Form:** This form asks participants about their baseline information including full name and date of birth and will be administered at the time of enrollment.
- **Quality of Life Questionnaires:** Health-related quality of life will be

assessed by items from the *European Organisation for Research and Treatment of Cancer* Quality of Life Questionnaire Comprehensive 30 (EORTC-QLQ-C30) and Quality of Life Questionnaire Lung Cancer 13 module (EORTC-QLQ-LC13), which will be administered to each patient participant at baseline, months 3, 6/off- study (+/- 4 weeks each). The EORTC is a well-established and frequently used questionnaire that includes a 5-item physical functioning domain, individual symptom items including symptoms specific to lung cancer patients, and a composite quality of life score.

- **Patient Satisfaction Survey:** The patient satisfaction survey will be administered to each participant at baseline and 6 months of participation (+/- 4 weeks). The satisfaction questions are from the Consumer Assessment of Healthcare Providers and Systems (CAHPS) survey system, which is maintained by the Agency for Healthcare Research and Quality (AHRQ), to support and promote the assessment of consumers' experiences with health care, and from the "Patient-Centered Communication in Cancer Care" short form and validated instrument (PCC-CA-6). No total score is calculated, but individual items will be summarized and reported.

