**2.2.1 Secondary Endpoints will be:**

1. Percentage of patients surveyed at 6 months on study satisfied with care team communication.
2. Health-related quality of life (HRQOL): change in comprehensive EORTC-QLQ30 and LC13 survey score from baseline at 6 months.
3. Overall Survival (from time of enrollment).
4. Percentage of surveys completed at each weekly delivery time point

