#### Off-Study Timing and Procedures

Participants are asked to remain on the study completing surveys for 6 months (26 weekly ePROs), or until they go off-study prior to that time. An "Off-study form" requiring information to be abstracted from the participant's medical record will be completed by the study coordinator when the participant goes off study (+ 4-week window for form completion). Consultation with MTOP physician or nurse may be necessary for clarifications of some of the questions in

this form. For example, this form includes information about reasons and timing for the reasons for going off-study. In addition, the final chart abstraction form will also be completed (see above) when going off study. In addition, if a patient goes off study early for any reason other than death, the coordinator will attempt to contact the patient to complete the final Outcomes Questionnaires (including: “Patient Quality of Life” and “Patient Satisfaction”) as soon as possible.

Some of the reasons for patients going off-study include:

- Completion of 6 months (26 weeks) of participation
- Initiation of hospice
- Death
- Moved to a different practice for lung cancer care
- Voluntary disenrollment
- Lost to follow-up
- Removal by principal investigator

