#### 4.5 Removal of Patients from Protocol

Patients will be removed from the study if:

- they experience significant emotional distress in response to mobile remote monitoring
- they indicate that they no longer wish to participate

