**Schedule of Activities:**

Study Procedures	- 4 week window		
	Baseline	Month 3	Month 6/Off-study
Informed Consent	X		
Eligibility Criteria	X		
Participant Demographics	X		
Moovcare® Registration and Training	X		
EORTC-QLQ-C30	X	X	X
EORTC-QLQ-LC13	X	X	X
Weekly Moovcare® ePRO symptom survey *	→		
Patient Satisfaction Survey	X		X
Provider Satisfaction Survey			X

\*Participants may also complete the Moovcare® ePRO symptom survey on an as needed basis

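### A living patient who goes off study before about week 22 has no scheduled month 6 quality-of-life survey, and section 7.3 does not say whether the early off-study survey counts as the 6-month value

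*Combined protocol and SAP*

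**What the plan says.** - **Endpoint.** Section 2.2.1 defines the HRQOL endpoint as "change in comprehensive EORTC-QLQ30 and LC13 survey score from baseline at 6 months".
- **Schedule.** Section 4.3 (Outcome Surveys) states that "HRQOL will be reassessed at months 3, 6/off-study (+/- 4 weeks each". The section 5.1 table has a single last column, "Month 6/Off-study", for both EORTC questionnaires and for patient satisfaction.
- **Early leavers.** The same part of section 4.3 says: "If the patient goes off study prior to week 26, the study coordinator will contact the patient as soon as possible". Under Off-Study Timing and Procedures, "if a patient goes off study early for any reason other than death, the coordinator will attempt to contact the patient" for the last set of quality-of-life and satisfaction questionnaires. No later survey is described.
- **Who goes off study.** Apart from completion and death, section 4.3 lists hospice, a move to another practice, voluntary disenrollment, loss to follow-up and removal by the investigator. Section 4.5 removes patients who are significantly distressed by monitoring, or if "they indicate that they no longer wish to participate".
- **Analysis.** Section 7.3 plans a paired t-test of the change from baseline to 6 months in the QLQ-C30. It leaves out patients who die before 6 months, carries month 3 forward as a sensitivity analysis when the 6-month survey is unanswered, and mentions exploratory longitudinal modelling. It does not refer to off-study surveys.

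**The concern.** The protocol has one off-study status. It does not provide for a patient who formally gives up weekly monitoring but would still complete a questionnaire at month 6. The last EORTC survey moves forward to the date of departure and shares a label with the true 26-week survey. An analyst could treat a week 5 survey as the 6-month value, or could treat the 6-month value as missing. The text supports neither choice over the other.

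Patients who enter hospice, disenroll or are removed plausibly differ in quality of life from those who stay. A change score from stayers only, or one with early values mixed in, would not describe 6-month survivors. Section 1.3 says the study should give preliminary data for later controlled studies of quality of life, so the estimate is meant to be used. A month 6 value that was never collected cannot be restored in the analysis.

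**Working it through.** The plan states no precision, power or dropout figure for HRQOL, so there is none to reproduce. The check covers timing first, then size.

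**1. Timing**
- Planned participation is 26 weekly surveys: 26 × 7 / 30.44 = 5.98 months, which agrees with 6 months.
- The month 6 window opens at 26 − 4 = week 22. An off-study survey from week 22 onward is a valid month 6 survey. One before week 22 is not.
- Taking month 3 as week 13, its window is 13 ± 4 = weeks 9 to 17. An off-study survey may fall before this window, inside it, or between it and week 22.

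**2. What section 7.3 does with a living patient who leaves early**

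| Off-study survey | Month 3 value to carry forward? | 6-month value under section 7.3 |
|---|---|---|
| Before week 9 | None scheduled | Missing, or the early value; not stated |
| Weeks 9 to 17 | Perhaps; the survey could be read as month 3 or as month 6/off-study | Not stated |
| Weeks 18 to 21 | Yes, if the month 3 survey was answered | Month 3 carried forward, or the early value; not stated |
| Week 22 onward | Not needed | Valid month 6 value |

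Only deaths are excluded, so living early leavers stay in the group the analysis describes. Carry-forward is a sensitivity analysis and does not help the first row. A longitudinal model can use an early value at its own date, but it must extrapolate to month 6.

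**3. Size (all rates assumed)**

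Let p be the share of 6-month survivors who left before week 22, and d the difference in mean 6-month change between leavers and stayers. The mean over all survivors is (1 − p) × stayers + p × leavers, so the stayers-only mean is off by p × d. With d = 10 points on the 0–100 scale:
- p = 5%: 0.05 × 10 = 0.5 points
- p = 15%: 0.15 × 10 = 1.5 points
- p = 30%: 0.30 × 10 = 3.0 points

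If early values are used instead, the error is p × (leavers' early change − leavers' true 6-month change).

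In patient numbers, take 50 enrolled and assume 10% deaths, which leaves 45 survivors. The last column is the detectable standardized change in a paired t-test (two-sided 0.05, 80% power, both assumed):

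| Living early leavers | Share of 45 | Shift at d = 5 / 10 / 15 | Month 6 values left | Detectable change |
|---|---|---|---|---|
| 0 | 0% | 0 | 45 | 0.43 |
| 5 | 11.1% | 0.6 / 1.1 / 1.7 | 40 | 0.45 |
| 10 | 22.2% | 1.1 / 2.2 / 3.3 | 35 | 0.49 |
| 15 | 33.3% | 1.7 / 3.3 / 5.0 | 30 | 0.53 |

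The table assumes that every remaining survivor answers at month 6.

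**The case against.** The strongest reply is that this is a single-arm feasibility study. Its secondary objective concerns quality of life in patients using the application, so a survey months after stopping answers a different question. Section 7.3 also has a carry-forward analysis and a longitudinal model. Few leavers may be recoverable, because those lost to follow-up cannot be reached and many who disenroll would decline. This limits the importance of the point and the yield of the fix. It does not settle how an early survey is analysed: section 7.3 is silent whichever question is intended.

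Three stronger readings are tempting, but the documents do not support them.
- **That stopping the weekly surveys is enough to end follow-up.** Non-response is not among the listed off-study reasons, and section 8.4.3 says non-adherence is not a deviation. A patient who merely skips weekly surveys remains due the month 3 and month 6 questionnaires.
- **That all outcome collection ends at off-study.** Sections 4.1 and 4.3 allow chart abstraction at any point after enrollment, and section 7.3 runs survival to last contact or death. The Off-study form itself is a chart-abstraction form; what takes the place of month 6 is the off-study EORTC administration. The one friction is that section 4.3 calls the abstraction at off-study *final*.
- **That withdrawn patients are pursued against their wishes.** Contact is attempted "if a patient goes off study early for any reason other than death", which includes the removals in section 4.5. The protocol text shows no step asking whether they accept contact. The consent form is not part of the text available for this review and may cover it, so this is not established.

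**Conclusion.** The point holds for living patients who formally go off study before about week 22. They have no scheduled month 6 EORTC survey, and the plan does not say whether the early survey stands in for it. Patient satisfaction at 6 months, another secondary endpoint, shares the combined slot and the same ambiguity. The primary completion-rate endpoint is untouched.

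The size cannot be established from the documents. The 0.5 to 3.0 points rest on an assumed early-leaving share of 5% to 30% of survivors and an assumed 10-point difference; with little early leaving or similar changes, the shift is negligible. The gap in the schedule and in the analysis rule does not depend on those assumptions. It should be corrected while month 6 values can still be collected.

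**What to change.** 1. **Sections 4.3 and 4.5.** When a patient goes off study, record whether they are stopping only the weekly surveys or declining further contact. Keep the scheduled month 3 and month 6 REDCap EORTC surveys for those willing, and make no further survey contact with those who decline.
2. **Section 5.1.** Split the combined column. Record the off-study EORTC survey as its own dated visit, separate from month 6.
3. **Section 7.3.** State that only surveys within 4 weeks of month 6 count as the 6-month value, and that earlier off-study surveys enter the longitudinal model at their actual dates. Report the number of survivors without a month 6 value, by reason.
4. **Section 4.3.** Reconcile the *final* chart abstraction at off-study with the provision elsewhere for abstraction at any point after enrollment.

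The cost is an amendment with matching consent wording where needed, one added item on the off-study form, and continued use of the existing REDCap e-mails and coordinator. Willing leavers answer a few more questionnaires. Response will be partial, and those who answer may not represent all leavers, so the fix reduces the gap without closing it.

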## 1.0 BACKGROUND AND RATIONALE

### 1.1 Study Synopsis

This single site study is being conducted to evaluate the feasibility and acceptability of monitoring lung cancer patients' disease- and therapy-related symptoms remotely with electronic patient-reported outcome (ePRO) surveys. Up to 50 patients undergoing treatment and/or surveillance for new or existing diagnoses of lung cancer at the University of North Carolina's Lineberger Comprehensive Cancer Center will be prospectively enrolled to the use of the mobile medical application Moovcare® for 6 months. Moovcare® automatically delivers ePRO surveys on common symptoms experienced by lung cancer patients. Results are stored in a secure web-based portal for provider review. Concerning survey responses are reported to a designated provider via an email alert.

This study will evaluate and report on: patient adherence with surveys, patient and provider satisfaction with Moovcare®, quality of life, and survival during the study period.

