### **1.3 Purpose and Rationale**

The purpose of this study is to demonstrate the feasibility and acceptability of using Moovcare® to monitor symptoms related to complications of treatment (surgery, radiotherapy, and/or chemotherapy) and disease recurrence in American lung cancer patients as well as to provide preliminary data to inform future controlled studies on the association of ePRO monitoring with clinical and quality of life outcomes.

The study of the implementation of mobile health information technology (HIT), such as Moovcare®, in diverse patient populations and settings is important to identify and solve barriers to uptake. This study will endeavor to show feasibility of ePRO HIT in patients receiving care at the University of North Carolina (UNC), a large public, academic hospital setting. In a separate UNC study looking at the feasibility and impact of ePRO monitoring for the initial 90 days after discharge from thoracic surgery (including lung resection for cancer), initial study experience suggests ePRO use is likely to be feasible in other patients with intrathoracic pathology including lung cancer patients. Evaluating compliance with longitudinal ePRO monitoring throughout the treatment and surveillance periods of lung cancer patients will allow protocols for use in multidisciplinary care to be developed.

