### **2.2 Secondary Objectives**

The secondary objectives of the study will be to evaluate the acceptability of Moovcare® (through patient and provider satisfaction surveys) and estimate the overall survival and change in the quality of life in patients using Moovcare®.

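### The patient acceptability objective for Moovcare has no visible endpoint that measures the application: the one listed concerns satisfaction with care-team communication

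*Combined protocol and SAP*

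**What the plan says.** Three places in the combined protocol and SAP set the target. Section 1.3 gives the purpose as to "demonstrate the feasibility and acceptability of using Moovcare". Section 1.1 says the study will report "patient and provider satisfaction with Moovcare". Section 2.2 makes it a secondary objective to "evaluate the acceptability of Moovcare® (through patient and provider satisfaction surveys". Section 7.1 also lists acceptability within the primary objective, next to feasibility and adherence.

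Section 2.2.1 lists one satisfaction endpoint: "Percentage of patients surveyed at 6 months on study satisfied with care team communication". The exploratory endpoints in 2.2.2 are redacted.

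Section 4.3 (Outcome Surveys) describes the patient instrument: "The satisfaction questions are from the Consumer Assessment of Healthcare Providers and Systems (CAHPS) survey system", a system whose stated role is "to support and promote the assessment of consumers' experiences with health care". The other named source is the PCC-CA-6, a short form on patient-centered communication. There is no total score, and items are summarized singly. On timing: "The patient satisfaction survey will be administered to each participant at baseline and 6 months of participation (+/- 4 weeks". The schedule in 5.1 labels the second occasion month 6/off-study.

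Section 7.3 places patient satisfaction at 6 months in the primary data analysis and provides descriptive statistics for it. It states no change from baseline, no response that counts as satisfied, and no level that would count as acceptable.

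**The concern.** The objective asks whether patients find the application acceptable. The visible endpoint asks whether they are content with how their clinicians communicate. The two can diverge. If the communication percentage is the only patient figure reported against this objective, a good result could be read as showing that Moovcare is acceptable when no patient was asked about it, and a poor result could be held against the application for reasons unrelated to it. Section 1.3 says the study should inform later controlled studies, so a misread acceptability result would carry forward into their design.

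**Working it through.** The plan gives no figure to reproduce here. Section 7.2 states a target of 50 patients and an expected 80% completion of assigned surveys. It gives no expected satisfaction rate, precision or threshold. The check is therefore a comparison of the text, link by link.

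1. **Objective to endpoint.** Sections 1.1, 1.3 and 2.2 name Moovcare as the thing judged. Section 2.2.1 names care-team communication. The object has changed.
2. **Endpoint to items.** The sources named in 4.3 cover experience of health care and patient-centered communication. Nothing is said about ease of use, burden or willingness to continue with the application.
3. **Items to timing.** The survey is given at enrollment, when patients are only being registered and trained on Moovcare (5.1). Items that can be answered then do not require use of the application, which agrees with step 2.
4. **Analysis.** There is one arm (7.1), and satisfaction is summarized descriptively (7.3). A single 6-month percentage does not separate the application's contribution from the level of communication already present.
5. **Can the two diverge?** Take two hypothetical patients. One stops answering the weekly surveys as too burdensome but is pleased with the clinicians, and counts as a success. The other likes the application but is unhappy with the team, and counts as a failure. The percentage can mislead in either direction.
6. **Other routes to acceptability.** Completion is the primary endpoint (2.1) and is also reported for each week (2.2.1), so abandonment will be seen. But 2.1 defines completion as feasibility, while 2.2 assigns acceptability to the satisfaction surveys. Completion is also supported by e-mail reminders, possible coordinator contact and caregiver help (4.3). The provider survey is described in 4.3 in terms of staff effort, and in the adverse-event subsection after 7.4 as covering providers' experience of the portal. It is not in the visible endpoint list and cannot speak for patients.

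**Precision, as illustration only.** The exact (Clopper-Pearson) 95% limits for x of n are: lower = the 0.025 quantile of Beta(x, n−x+1); upper = the 0.975 quantile of Beta(x+1, n−x). The rates of 70%, 80% and 90% are assumptions, as are 40 and 30 respondents; 50 is the full target.

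| Respondents | 70% | 80% | 90% |
|---|---|---|---|
| 50 | 55.4–82.1% | 66.3–90.0% | 78.2–96.7% |
| 40 | 53.5–83.4% | 64.4–90.9% | 76.3–97.2% |
| 30 | 50.6–85.3% | 61.4–92.3% | 73.5–97.9% |

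These limits depend only on x and n. They would be the same for an application item as for a communication item, so redirecting the endpoint loses no precision at a given number of respondents. Nor does precision repair a mismatch of construct.

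**The case against.** The strongest reply is that the visible text is not the whole plan. The exploratory endpoints and part of the exploratory analyses are redacted, and the survey forms are appendices that are not available here. Section 4.3 names the survey systems the items come from, not the items chosen. The adverse-event subsection, in a sentence about patients, refers to surveys that give feedback on the electronic reporting system. Provider satisfaction is collected and analysed without appearing in the visible endpoint list, so that list is not a full inventory. All of this stands: application items may already exist, and no one should conclude that they do not.

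Second, abandonment is well covered. Besides completion, the plan records reasons for refusal and for going off study, and compares patients who complete more than 75% of surveys with the rest. This stands too. A burdensome application would leave traces, although the protocol does not label them acceptability.

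Third, a reader might infer that giving the survey before any use of Moovcare is a flaw. It is not. It is what makes a before-and-after comparison of communication possible, and communication is a sensible outcome for a system that sends symptoms to the care team.

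Fourth, a reader might infer that patients who quit are left out. Section 4.3 says otherwise: the coordinator tries to obtain the final satisfaction survey from anyone leaving early other than by death. What remains is an ambiguity, because the endpoint's wording does not clearly include those responses.

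Finally, no decision rule hangs on this endpoint, so no decision error can be computed. That limits the weight of the point but does not remove the mismatch.

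**Conclusion.** The point holds in a limited form. The percentage satisfied with care-team communication, reported descriptively at 6 months in one arm, does not by itself measure patient acceptability of Moovcare, and no other visible endpoint is assigned to that objective on the patient side. The stronger reading, that the trial cannot show whether Moovcare is acceptable, is not supported: the redactions, the unseen forms and the reference to feedback surveys leave room for application items, and the completion data bear on the question.

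The defect has no numerical size. The conclusion rests on the endpoint wording in 2.2.1 and the item sources in 4.3, and on the assumption that the communication percentage would otherwise be the patient result reported against the objective. It is an inexpensive improvement that lets the trial answer a question it sets itself.

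**What to change.** - In 2.2.1, name as the patient acceptability endpoint the percentage of patients agreeing on Moovcare-specific items: ease of use, burden, and willingness to continue or recommend. State which responses count as agreement.
- If the survey already has such items, use them. Otherwise add two to four to the existing month 6/off-study REDCap survey.
- State that off-study responses from patients who leave early count in the denominator.
- Report care-team communication separately, as change from the baseline already collected.
- If no application items exist and none can be added, do not draw a patient acceptability conclusion from the communication endpoint.

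The cost is about one more minute on a survey now listed at 3 minutes, plus an IRB amendment. If items have to be added, patients already past month 6 will lack them, and the report should give the number who were asked. If the items already exist, the change is one of wording and analysis only.
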